## 10.2 Individual Clinical Signs/Symptoms

At each clinic visit (except Visit 1/Screening), overall severity of erythema, scaling, fissuring, and papulation/lichenification will be graded for each TA using a five-point scale where 0=clear, 1=almost clear, 2=mild, 3=moderate, and 4=severe. This is a static morphological scale that refers to a point in time and not a comparison to Baseline.

ERYTHEMA		
0	Clear	No redness
1	Almost Clear	Faint red coloration predominates
2	Mild	Light red coloration predominates
3	Moderate	Moderate red coloration predominates
4	Severe	Dusky to deep red coloration predominates

SCALING		
0	Clear	No evidence of scaling
1	Almost Clear	Limited amount of very fine scales, little of the TA is affected
2	Mild	Mainly fine scales predominate, less than half of TA is affected
3	Moderate	Somewhat coarser scales predominate, greater than half of the TA is affected
4	Severe	Coarse, thick, tenacious scales predominate, virtually all of the TA is affected

FISSURING		
0	Clear	No evidence of fissuring
1	Almost Clear	No more than a very slight fissuring predominates, often easier felt than seen, little of the TA is affected
2	Mild	Mainly mild fissuring predominate, less than half of TA is affected
3	Moderate	Mainly moderate fissuring predominate, greater than half of the TA is affected
4	Severe	Mainly severe fissuring predominate, virtually all of the TA is affected

PAPULATION AND/OR LICHENIFICATION		
0	Clear	No evidence of plaque elevation above normal skin level.
1	Almost Clear	Very slight elevation above normal skin level predominates, easier felt than seen, little of the TA is affected.
2	Mild	No more than a slight ( $\leq 1$ mm) but definite elevation of focal skin areas due to papulation and/or lichenification predominates; less than half of the TA is affected
3	Moderate	No more than a moderate ( $\leq 2$ mm) elevation of focal skin areas due to papulation and/or lichenification predominates; greater than half the TA is affected
4	Severe	Marked elevation ( $> 2$ mm) of papulation and/or lichenification predominates; virtually all of the TA is affected.

### 10.3 Fitzpatrick Skin Type Assessment

At Visit 1, the investigator or designee will document the subject's skin phototype (I-VI) using the Fitzpatrick Skin Type Assessment.

Fitzpatrick Skin Type Assessment		
Phototype	Typical Features	Tanning Ability
I	Pale white skin, blue/hazel eyes,	Always burns, does not tan
II	Fair skin, blue eyes	Burns easily, tans poorly
III	Darker white skin	Tans after initial burn
IV	Light brown skin	Burns minimally, tans easily
V	Brown skin	Rarely burns, tans darkly easily
VI	Dark brown or black skin	Never burns, always tans darkly

### 10.4 Local Skin Reactions

At each clinic visit (except Visit 1/Screening), LSRs including burning/stinging, pain, and pruritus will be documented in each Treatment Area using a four-point ordinal scale where 0=none, 1=mild, 2=moderate, and 3=severe. These LSRs will be collected independently

of AEs. Only LSRs that require medical intervention (e.g., prescription medication) or require withholding or reduction in dosing frequency of the test articles will be documented as AEs. Any LSRs that are not listed above will be recorded as AEs.

## **11. PHOTOGRAPHY**

Photography documentation is required in this study at Visit 2/Baseline/Day 1, Visit 6/Day 29, Visit 8/Day 57, and Visit 9/Day 84. Copy(s) of the Baseline photos may be provided to the subject, at the discretion of the investigator, to help the subject consistently identify the two Treatment Areas. Photographs may also be taken at other visits at the discretion of the investigator. Photographs taken as part of this study will be used to document the effects of treatment, AEs, or other findings during the study. The site will be provided with suggested guidelines to assist them in taking standardized photographs. Photographs will be taken of lesions only, without including subject identity (i.e., facial photos). All photographs taken as part of this study are for informational purposes only and are not to be used in grading or for any other assessment.

Note: Subjects may decline to have photographs taken during the conduct of the study. If a subject initially consents to photographs, then declines further photography, the Sponsor may use the photographs taken under consent for the purposes noted above.

## **12. LABORATORY TESTS**

### **12.1 Blood Chemistries, Hematology and Urinalysis**

Blood and urine specimens will be collected at Visit 1/Screening, Visit 6/Day 29, Visit 8/Day 57 (End of Part 1), and Visit 9/Day 84 (EOT or early termination) for chemistry, hematology, and urinalysis. Subjects must be fasting (approximately 8 hours) for screening laboratory tests and, if possible, for laboratory tests at Visit 6/Day 29, Visit 8/Day 57, and Visit 9/Day 84; however, if a subject arrives at the clinic for Visit 6, Visit 8, or Visit 9 without fasting for at least eight hours, laboratory specimens may be collected as non-fasting, at the discretion of the investigator, and with the appropriate fasting status documented on the lab requisition form.

The following tests will be performed

Chemistries	Hematology	Urinalysis
Albumin	Hemoglobin	Blood
Alkaline Phosphatase	Hematocrit	Glucose
ALT (SGPT)	MCV	Ketone
AST (SGOT)	MCH	pH
Bicarbonate	MCHC	Specific Gravity
Bilirubin, total	RBC (Erythrocytes)	Microscopic Analysis
Calcium	WBC (Leucocytes)	WBC
Chloride	RDW	RBC
Cholesterol	Differential count	Casts
Creatinine	Basophils	
GGT	Eosinophils	
Glucose (fasting)	Lymphocytes	
LDH	Monocytes	
Potassium	Neutrophils	
Phosphate	Platelets	
Protein, total		
Sodium		
Triglycerides		
Urea (BUN)		
Uric Acid		

Sample collection, handling, labeling, and shipping should be done following the instructions provided by the relevant certified laboratory and the applicable local regulations.

The investigator must review all the subject’s laboratory reports in a timely manner. **NOTE:** The investigator will initial and date each laboratory report to indicate his/her review. The investigator will note, directly on the laboratory report, whether or not any abnormal test results are clinically significant. The investigator must complete an appropriate AE form for any new or worsening abnormal test results that are identified as clinically significant after Baseline.

AEs that may be associated with venipuncture and that must be included in the informed consent include:

- Pain
- Bruising
- Bleeding at the puncture site
- Fainting
- Inflammation of the vein

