### 9.1 Visit 1 (Day -45 to -7): Screening

Subjects can be screened for the study up to 45 days before Visit 2. If applicable, qualified subjects can washout from prohibited medications or treatments prior to Visit 2 (after obtaining consent/assent). Subjects that require washout for longer than 45 days will be re-consented. Clinical laboratory tests will be performed after the subject has fasted (for approximately eight hours).

*At Screening, the investigator or designee will:*

- Obtain a signed, written informed consent (unless the subject signed a consent within the past 45 days). Note: Subjects under 18 years of age must provide written informed assent and be accompanied by the parent and legal guardian at the time of assent/consent signing. The parent or legal guardian must provide informed consent for the subject. If a subject becomes 18 years of age during the study, the subject must provide written informed consent at the time to continue study participation.
- Record demographics.
- Confirm I/E criteria.
- Confirm the subject has qualified analogous right and left Treatment Areas, with adequate disease ( $\geq 150$  cm^2) and identical IGA scores ( $\geq 3$ ) consistent with the I/E criteria (see Section 5.1) that will likely meet protocol requirements and Baseline, in the opinion of the investigator.
- Record medical/ichthyosis history.
- For those subjects who do not have confirmation of their clinical diagnosis of X-linked or lamellar ichthyosis, collect blood or buccal samples for genetic testing (see Section 12.4).
- Record prior and/or concomitant medications and therapies.
- Perform brief physical exam. Record any findings in the medical history.
- Perform vital signs (heart rate, respiration rate, blood pressure, and temperature), and height/weight.
- Perform UPT for WOCBP. Results must be negative for the subject to be enrolled in the study.

- Perform Fitzpatrick Skin Type assessment.
- Collect urine and blood samples for clinical laboratory tests.

QUALIFIED SUBJECT DETERMINATION AND TEST ARTICLE REQUEST: Prior to Visit 2/Baseline, after clinical laboratory results have been received and reviewed, and the investigator has confirmed the subject's eligibility, the site will contact the subject to confirm their willingness to participate in the treatment phase of the study. Assuming the qualified subject is willing to participate, then the site will:

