#### 9.5 Visit 6 (Day 29 $\pm$ 3): Follow-Up

*At this visit the investigator or designee will:*

- Query the subject about any changes in health status since the previous visit, including concomitant medications and therapies, and document the findings.
- Perform brief physical exam. Record any new or worsening findings as AEs.

- Perform vital signs (heart rate, respiration rate, blood pressure, and temperature).
- Perform UPT for WOCBP. Results must be negative for the subject to continue in the study.
- Collect urine and blood samples for clinical laboratory tests. If possible, subject will have fasted for approximately eight hours or more prior to these laboratory tests.
- Perform IGA for each Treatment Area.
- Assess CI Signs/Symptoms for each Treatment Area.
- Document LSRs for each Treatment Area.
- Update Concomitant Medications and Therapies, as applicable.
- Take photographs.
- For those subjects participating in the PK portion of the study, collect PK blood sample PRIOR to application of the test articles. Note: This sample will be collected 12 hours  $\pm$  30 minutes after the dose on the previous day.
- Document test article accountability; weigh the tubes and return/dispense the test articles, as applicable.
- Review compliance and collect/dispense Subject Diary, as applicable.
- **Review proper test article use and application guidelines with the subject (and parent/legal guardian, if applicable), stressing the importance that care should be taken that the correct test article is applied to the two Treatment Area(s) on the subjects RIGHT and LEFT side.**
- If possible, supervise the application of the test articles. The test article with the **RED** label should be applied to the **RIGHT** Treatment Area and the test article with the **LEMON YELLOW** label should be applied to the **LEFT** Treatment Area.
- Document any AEs.
- Schedule Visit 7 (Phone Call; see [Section 9.3](#)) and Visit 8 (Clinic Visit).

## 9.6 Visit 8 (Day 57 $\pm$ 4): End of Part 1

*At this visit the investigator or designee will:*

- Query the subject about any changes in health status since the previous visit, including concomitant medications and therapies, and document the findings.
- Perform brief physical exam. Record any new or worsening findings as AEs.
- Perform vital signs (heart rate, respiration rate, blood pressure, and temperature).
- Perform UPT for WOCBP. Results must be negative for the subject to continue in the study.

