### 17.2 Endpoints

#### 17.2.1 Safety Endpoints

Safety endpoints will include:

- Incidence (severity and causality) of any local and systemic AEs
- Number of subjects with presence (and severity) of the following LSRs: stinging/burning, pain, and pruritus at each time point for each Treatment Area collected (summarized by Test Article).
- Changes from Screening in vital signs at Days 29, 57, and 84 (or EOT) (summarized by Treatment Group).
- Changes from Screening in clinical laboratory tests (hematology, chemistry, and urinalysis) at Days 29, 57, and 84 (or EOT) (summarized by Treatment Group).
- UPT results in all WOCBP at Screening, Baseline, Day 29, Day 57, and Day 84 (or EOT).

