#### Clinical Laboratory Tests

Clinical laboratory data (hematology, chemistry, and urinalysis) will be tabulated at Screening and Days 29, 57, and 84. Changes from Screening in laboratory data at Days 29, 57, and 84 will also be summarized. All laboratory data will be listed and reported in the units received by the central laboratory. Shift tables by analyte and by out of range flag will be presented to facilitate the evaluation of change from Screening to Days 29, 57, and 84.

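### Screening labs must be fasting but Day 29, 57 and 84 labs need not be, and the change and shift tables ignore fasting status; any non-fasting samples would push mean triglyceride and glucose changes upward

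*Combined protocol and SAP*

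**What the plan says.** Section 12.1 sets the Screening rule: "Subjects must be fasting (approximately 8 hours) for screening laboratory tests". Section 9.1 repeats it. By the Schedule of Events, Screening is the only laboratory sample before treatment, so it is the reference for every change.

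At the on-treatment visits the rule is softer. Section 9.5 (Visit 6) says: "If possible, subject will have fasted for approximately eight hours or more prior to these laboratory tests". Sections 9.6 and 9.7 say the same for Visits 8 and 9. For a subject who arrives without having fasted, Section 12.1 provides that "laboratory specimens may be collected as non-fasting, at the discretion of the investigator", "with the appropriate fasting status documented on the lab requisition form".

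Section 17.2.1 lists laboratory change from Screening, by Treatment Group, as a safety endpoint. Under Clinical Laboratory Tests, Section 17.3.1 says: "Changes from Screening in laboratory data at Days 29, 57, and 84 will also be summarized". It adds: "Shift tables by analyte and by out of range flag will be presented". The Synopsis matches. None of these places conditions on fasting status, splits by it or flags it. Triglycerides and glucose are both on the Section 12.1 panel.

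**The concern.** The mismatch can run only one way: a fasting reference is compared with a value that may be non-fasting. For analytes that rise after food, that is a possible bias and not only extra noise. The point is limited to triglycerides and glucose. Their upward direction after food is general physiology, not something the documents state.

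The study has no internal check on it. Sections 4 and 6.1 put active ointment on one side of every subject in Part 1 and on both sides in Part 2. The vehicle side is a control for local reactions but not for blood chemistry. Safety is the primary objective, and Section 14.1 says the ointment has not been studied in humans before. A food effect could therefore be reported as an on-treatment rise, with nothing in the tables to suggest another cause.

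**Working it through.** The plan states no figure to reproduce: Section 17.1 has no power calculation, and no laboratory standard deviation (SD) or effect size is given. From the documents come the fasting rules, the tables and about nine subjects per group (Synopsis). Everything else below is assumed, with no drug effect.

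**Assumptions.** Each on-treatment sample is non-fasting with probability f, independent of the subject's level; f is 0, 10% or one third.
- Triglycerides: median 95 mg/dL, between-subject log-SD 0.40, within-subject log-SD 0.14, upper limit 150 mg/dL, food increment 15% to 50%.
- Glucose: mean 90 mg/dL, between-subject SD 6, within-subject SD 5, upper limit 99 mg/dL, food increment 5 to 30 mg/dL.

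**Mean bias.**
- Triglycerides: the fasting mean is 95 × exp((0.40² + 0.14²)/2) = 103.9 mg/dL, and the bias is f × increment × 103.9. At 10%: 0.10 × 0.15 × 103.9 = 1.6, up to 0.10 × 0.50 × 103.9 = 5.2. At one third: 5.2 to 17.3.
- Glucose: the bias is f × increment. At 10%: 0.5 to 3.0. At one third: 1.7 to 10.0.

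**Against the standard error (SE) at n = 9.** The SE uses the spread of the mixed fasting and non-fasting data. For glucose the variance of change is 2 × 5² + f(1 − f) × increment². At 10% and 30 mg/dL that is 50 + 81 = 131, so SE = √131/3 = 3.8 and the ratio is 3.0/3.8 = 0.79. Triglyceride SEs and all medians come from simulation with 2,000,000 subjects per setting.

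| | f = 0 | f = 10% | f = one third |
|---|---|---|---|
| Triglycerides: mean bias, mg/dL | 0 | +1.6 to +5.2 | +5.2 to +17.3 |
| in SEs | 0 | 0.20 to 0.54 | 0.64 to 1.41 |
| expected median change (n = 9) | 0 | +1.2 to +2.7 | +4.3 to +11.9 |
| normal-to-high shifts expected per 9 | 0.37 | 0.43 to 0.62 | 0.56 to 1.19 |
| Glucose: mean bias, mg/dL | 0 | +0.5 to +3.0 | +1.7 to +10.0 |
| in SEs | 0 | 0.21 to 0.79 | 0.67 to 1.90 |
| normal-to-high shifts expected per 9 | 0.66 | 0.79 to 1.37 | 1.08 to 3.05 |

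With three increments per analyte (15, 25, 50%; 5, 10, 30 mg/dL) and two non-zero shares there are 12 settings. Three exceed one SE, all at one third: triglycerides at 50% (1.41), and glucose at 10 mg/dL (1.18) and 30 mg/dL (1.90).

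**Sensitivity to the glucose limit.** With everyone fasting, expected shifts per nine are 0.66 at a limit of 99 mg/dL, 0.185 at 105 and 0.04 at 110. At 10% and 5 mg/dL they are 0.79, 0.24 and 0.06. Large increments depend on the limit much less: at one third and 30 mg/dL they are 3.05, 2.96 and 2.71.

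**How often it could arise.** At f = 10%, the chance of at least one non-fasting sample in a group of nine at a visit is 1 − 0.9⁹ = 61%. The chance that the two groups differ by two or more non-fasting subjects is 22%.

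**Dose contrast.** With equal shares the spurious difference is zero. With 1 of 9 against 3 of 9 non-fasting, the triglyceride difference is (3/9 − 1/9) × (0.15 to 0.50) × 103.9 = 3.5 to 11.5 mg/dL.

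**The case against.** The strongest reply is that this is small and partly handled already.
- **Size.** At 10% non-fasting no setting reaches 0.8 SE, and the extra triglyceride shifts are 0.06 to 0.25 of a subject per nine. This stands.
- **Likely share.** Nothing in the documents supports one third. Fasting is requested at each visit, Section 9.3 has subjects hold the morning application on clinic days, and pharmacokinetic samples follow the previous day's dose by about 12 hours. Morning visits after an overnight interval are a fair inference, so the low end is more plausible.
- **The planned median.** Section 17.3 reports it beside the mean, and a minority of non-fasting samples moves it less. It reduces the bias without removing it. The minimum, maximum and standard deviation could also show extra spread, but not its cause.
- **Review and listings.** Investigators judge each abnormal result, and all laboratory data are listed for about 18 subjects. That may prevent false adverse events, but it does not correct the tables.
- **No unexposed group.** This limits every within-group laboratory change here and is not a fasting defect in itself. It matters because it removes the usual way of recognising a food effect.

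A reader might go further and infer that the laboratory safety results will be biased, that the comparison of 0.1% with 0.2% is compromised, or that the listings will omit fasting status. The documents support none of these. They give no non-fasting rate; the dose contrast is unbiased when shares are equal; and the listing columns are not specified either way.

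**Conclusion.** The asymmetry is in the current text, and the planned summaries make no use of the fasting status that the sites record. If non-fasting samples occur, the mean triglyceride and glucose changes and the normal-to-high shift counts lean upward within each Treatment Group. Under the stated assumptions the lean is negligible to modest at 10% non-fasting. It exceeds one standard error only at a one-third share with the larger increments, and it vanishes if all subjects fast. The small-increment glucose shift counts should not be quoted without the assumed upper limit.

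The summaries are descriptive, so no error rate, test or sample size is affected. Priority is low to moderate: a conditional weakness worth closing because the information is already collected.

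**What to change.** Transfer fasting status from the requisition form to the laboratory dataset and flag non-fasting values in the listings. Add to Section 17.3.1 (Clinical Laboratory Tests) and to the Synopsis:

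*For triglycerides and glucose, changes from Screening and shift tables will be presented for all samples and repeated for fasting samples only.*

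Any rise in the all-samples table would then be read beside the fasting-only table. No visit procedure changes and no data are dropped.

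The cost is one variable, one listing flag, one sentence in two places and one set of companion tables for two analytes. The listing flag alone would make the cause of an individual value traceable; the companion tables are what remove the food effect from the summaries, giving a mean change of zero in every no-drug-effect setting above.

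The fasting-only tables rest on fewer subjects. At 10% non-fasting about 8 of 9 remain, with a triglyceride SE of 22.4/√8.1 = 7.9 mg/dL; at one third, 6 of 9 remain, with 22.4/√6 = 9.1. Here 22.4 mg/dL is the SD of change when all samples are fasting. The all-samples SEs are 7.7 to 9.6 and 8.2 to 12.3. The fasting-only tables also select on behaviour after randomization, so they should accompany the all-samples tables and not replace them.

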## 12.2 Urine Pregnancy Tests

UPTs must be performed on all WOCBP at Visit 1/Screening, Visit 2/Day 1 (prior to

randomization), Visit 6/Day 29, Visit 8/Day 57, and Visit 9/Day 84 (EOT or early termination); UPTs must be negative for the subject to be eligible for and to continue in the study. The UPTs will be performed at the study site, if the site is registered and conforms to CLIA regulations for such testing (possesses a current valid CLIA Certificate of Waiver), or at an appropriately registered reference laboratory. The investigator will report the UPT results on the CRFs, in the subject's medical records, and in independent records maintained at the study site. The UPT used must have a minimum sensitivity of 25 mIU of  $\beta$ -HCG/mL.

### **12.3 Pharmacokinetic Sample Collection, Storage, and Assay**

At Visit 2/Day 1, PK blood samples will be collected for isotretinoin and tretinoin pre-test article application (time 0) and at 1, 2, 3, and 4 hours post-test article application. At Visit 4/Day 8, Visit 5/Day 15, Visit 6/Day 29, Visit 8/Day 57, and Visit 9/Day 84, a PK blood sample will be collected for isotretinoin and tretinoin pre-test article application (approximately 12 hours after the last test article application on the previous day). Sampling times will be recorded on the appropriate CRFs. Site (e.g., right versus left arm) of PK blood draws will be recorded.

The method of sample collection for PK analysis is detailed in the laboratory manual to be provided by the laboratory vendor. Each PK blood sample will be processed and stored as detailed in the laboratory manual. Samples will be prepared in duplicate; one of the samples will be shipped to the analytical laboratory using an authorized courier and the other sample will be stored at the site as back-up samples until confirmation that the initial shipment has been safely received by the analytical laboratory. Details and specific instructions on labeling and management of these specimens are provided in the laboratory manual.

Plasma will be analyzed for levels of isotretinoin and tretinoin and compared to background systemic retinoid levels pre- and post-treatment.

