## **6. TEST ARTICLES AND REGIMEN**

### **6.1 Description**

PAT-001 is a pale yellow, viscous ointment. Vehicle ointment is color matched to the active test article. In Part 1, each subject shall receive two test articles: a vehicle ointment and an active ointment product (either 0.1% or 0.2% PAT-001) for treatment to the left and right Treatment Areas. The test articles will be blinded using color coded labeling as detailed in [Section 6.2](#) and [Appendix 1](#) to facilitate proper use during the study period. In Part 2, each subject will receive the active ointment product assigned in Part 1 for both Treatment Areas.

Test Article Name: PAT-001 (isotretinoin) Ointment, 0.1%  
Active ingredient: isotretinoin, USP  
Other ingredients: super refined polyethylene glycol (PEG) 400, PEG 1450, PEG 3350, methylparaben, butylated hydroxytoluene, and propyl 4-hydroxybenzoate, propylparaben

Test Article Name: PAT-001 (isotretinoin) Ointment, 0.2%  
Active ingredient: isotretinoin, USP  
Other ingredients: super refined PEG 400, PEG 1450, PEG 3350, methylparaben, butylated hydroxytoluene, and propyl 4-hydroxybenzoate, propylparaben

Test Article Name: Vehicle Ointment  
Other ingredients: super refined PEG 400, PEG 1450, PEG 3350, methylparaben, butylated hydroxytoluene, and propyl 4-hydroxybenzoate, propylparaben; color additive

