## 6.2 Instructions for Use and Application

At Visit 2/Baseline, the investigator will designate two comparable Treatment Areas. Each Treatment Area shall be contained within a discrete anatomic unit (e.g., upper arm, forearm, upper leg, lower leg) with bilateral involvement and a minimum of 150 cm^2 in area of diseased skin that shall not exceed 6% BSA; these Treatment Areas will be selected for treatment and designated by right and left sides. Both Treatment Areas must have comparable area of disease involvement and have the same IGA score of 3 (moderate) or 4 (severe) at Visit 2/Baseline. Note: Palms and soles are not eligible; the treatment of scalp and skin folds/intertriginous regions should be avoided. Additionally, for those subjects participating in the PK portion of the study, treatment on the arms, the antecubital fossa (e.g., approximately 10-15 cm^2) will be excluded to minimize contamination of PK blood draws. Location by body region and percent BSA of disease affected skin in each Treatment Area at Baseline will be documented.

Subjects will be provided with an instruction sheet detailing how to apply the test articles (see [Appendix 1](#)) and a study staff member will demonstrate how to dispense and apply the test articles. If the subject is a minor, the parent/legal guardian will be given the Subject Instructions with their child and instructed to apply or supervise application on the subject; the level of involvement (i.e., application vs. supervision) by the parent/legal guardian will be determined by the investigator. Note: For Part 1, the test articles will be blinded using color coded labels to designate which test article to apply to each Treatment Area: **RED = Right and **LEMON YELLOW = Left.****

Subjects (and parent/legal guardians, if applicable) will be instructed to wash their hands before and after each test article application. Subjects (and parent/legal guardians, if applicable) will be instructed to wash the Treatment Areas with a mild non-medicated cleanser and water and then to dry the area gently. Subjects (with parent/legal guardian supervision, as required) will be instructed to apply a sufficient amount of the test article to provide a thin uniform film over the disease affected skin within the Treatment Area

---

 FD&C Yellow #3 and FD&C Blue #2.

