## **15. BLINDING/UNBLINDING**

Blinding is important for the integrity of this clinical study. However, the blind may be broken in the event of a medical emergency in a subject, in which knowledge of the test article identity is critical to the subject's management. Before breaking the blind for a subject, the investigator should determine that the information is necessary (i.e., that it will

alter the subject's immediate management). In many cases, particularly when the emergency is clearly not test article related, the problem may be effectively managed by assuming that the subject is receiving active product without the need for unblinding. The need to break the blind should first be discussed with the responsible Medical Monitor and the best method to do this will be determined.

In Part 1, the test articles will be blinded using color coded labels to designate which test article to apply to each Treatment Area.

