#### Trough Concentrations

Trough plasma concentrations of isotretinoin and tretinoin at Days 8, 15, 29, 57, and 84 will be compared between Treatment Groups.

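### In PK subjects treated on the forearm, blood may be drawn from a vein draining active-treated skin, and the recorded draw site is not used in the PK analysis

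*Combined protocol and SAP*

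**What the plan says.** **Where treatment may go.** Section 6.2: "Each Treatment Area shall be contained within a discrete anatomic unit (e.g., upper arm, forearm, upper leg, lower leg"). The same section has a special rule for PK subjects treated on the arms, so the sponsor foresees that case.

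**What is applied.** Section 6.1: "In Part 1, each subject shall receive two test articles: a vehicle ointment and an active ointment product", one on each side. Then: "In Part 2, each subject will receive the active ointment product assigned in Part 1 for both Treatment Areas". Section 15 adds that in Part 1 "the test articles will be blinded using color coded labels", so site staff do not know which side is active.

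**The stated safeguard.** For PK subjects treated on the arms, about 10-15 cm² at the antecubital fossa "will be excluded to minimize contamination of PK blood draws" (section 6.2; also section 9.2 and the Schedule of Events footnote on selecting Treatment Areas).

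**The draw site.** Section 12.3: "Site (e.g., right versus left arm) of PK blood draws will be recorded". It does not say which arm to use, or whether a treated limb may be used. It also says: "The method of sample collection for PK analysis is detailed in the laboratory manual to be provided by the laboratory vendor".

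**The analysis.** Section 17.3 limits the PK population by participation and dosing compliance only. Section 17.3.3 summarises the Day 1 concentrations by subject and compares Treatment Groups. For the later samples: "Trough plasma concentrations of isotretinoin and tretinoin at Days 8, 15, 29, 57, and 84 will be compared between Treatment Groups". Draw site appears in none of these, nor in the synopsis.

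**The concern.** The PK objective (section 3) is to see what topical PAT-001 adds to background systemic retinoid levels. A sample from a vein that drains treated skin measures the systemic level plus drug just absorbed locally. Leaving the elbow crease bare prevents contamination by the needle; it does not change what the vein has collected from the forearm below it.

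In Part 1, whether an arm draw is affected depends on the allocated side, which the person drawing does not know. In Part 2 both sides are active. Analysed as written, the plan mixes affected and unaffected samples in one summary.

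Three readings are at stake: the level of systemic exposure, which section 14.1 expects to be low; its course over time; and the comparison of 0.1% with 0.2%. The PK portion is an optional part of a trial of about 18 subjects, and the summaries include the mean and maximum, so a few affected samples could carry weight.

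**Working it through.** The plan states no figure on this point, so there is none to reproduce. The check is of the text, followed by two illustrations.

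**1. Which samples can be affected**
- The Day 1 time 0 sample precedes any application, so it cannot be affected.
- The Day 1 samples at 1-4 h are taken while ointment is on the skin, because section 6.2 tells subjects not to wash the area for at least four hours.
- Samples on Days 8, 15, 29 and 57 can be affected if drawn above active-treated skin on the same limb.
- On Day 84 any elbow draw in a forearm-treated subject is affected, because both forearms are active.
- An elbow draw in a subject treated on the upper arm is largely outside the mechanism, because that skin lies above the draw point. Subjects treated on the legs and bled from an arm are outside it altogether.

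**2. How often, in a forearm-treated subject bled at the elbow (illustration)**

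Assume a blinded choice of arm, with probability 0.5 per visit of hitting the active side in Part 1.
- Arm chosen afresh at each of the 4 Part 1 trough visits: chance of at least one active-arm draw = 1 − 0.5⁴ = 93.8%; expected number = 4 × 0.5 = 2.
- Counting Day 1 post-dose as well (5 visits): 1 − 0.5⁵ = 96.9%.
- Same arm throughout Part 1: 50%.
- Day 84: 100%.

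**3. How large (assumption only)**

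Let CL be clearance, Q the venous flow at the sampled site, and k = CL/Q. None of these is in the documents. Assume steady state and that all drug absorbed from the limb drains through the sampled vein.
- One active area: absorption rate R = CL × Css, and the local increment is R/Q = k × Css. Measured/systemic = 1 + k.
- Two equal active areas: Css = 2R/CL, and the increment from one limb is R/Q = (k/2) × Css. Measured/systemic = 1 + k/2.

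| Assumed k | One active area | Two active areas |
|---|---|---|
| 0.1 | 1.1 | 1.05 |
| 0.5 | 1.5 | 1.25 |
| 5 | 6 | 3.5 |
| 10 | 11 | 6 |

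These ratios apply to the drug-derived part only. With background B, the reported value is inflated by 1 + k × Css/(B + Css) for one active area, which is less than 1 + k. The model does not size the Day 1 samples, which are not at steady state, and at 12 h after a dose the local part may be smaller.

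**4. Day 57 to Day 84**

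Under the same model with linear kinetics and equal areas, the true drug-derived level goes from 1 to 2, because the active-treated area doubles. The Day 84 arm draw reads 2 + k.
- Day 57 draw from the vehicle arm: apparent ratio = 2 + k, which is 2.5 at k = 0.5 and 7 at k = 5. The rise is exaggerated.
- Day 57 draw from the active arm: apparent ratio = (2 + k)/(1 + k), which is 2.5/1.5 = 1.67 at k = 0.5 and 7/6 = 1.17 at k = 5. The rise is hidden.

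The same true change is therefore reported too high or too low according to a field that the analysis does not use.

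**The case against.** **Scope.** The mechanism reaches mainly forearm areas, in an optional PK portion. The number of such subjects is not stated and could be zero. This stands, and the point is limited accordingly.

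**The laboratory manual.** Collection method is left to a manual not available here, which may already restrict the site. This also stands. The protocol's silence does not show that staff switch arms or draw from treated limbs; it shows only that the protocol allows it.

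**What the analysis claims.** Section 17.3.3 does not label the concentrations as systemic, and nothing prevents a listing by draw site. That is fair, but sections 3 and 12.3 set the purpose as comparison with background systemic levels, and no use of the draw site is planned.

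**Conservatism.** Overstating exposure errs on the safe side. That holds for the level. It does not hold for change over time, which can be hidden, or for the comparison of concentrations if draw sites differ between small groups.

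**Stronger readings.** A reader might infer that exposure will be overstated by some definite multiple, such as 1.5 to 6 times. The documents do not support one: k is assumed, complete drainage through the sampled vein is assumed, and with both areas active the same assumed range gives 1.25 to 3.5. A reader might also infer that Day 84 will show false accumulation. Part 2 doubles the active-treated area, so a real rise is to be expected, and the error can go either way.

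**Conclusion.** The point holds in limited form. The protocol permits PK draws downstream of active-treated forearm skin, its stated safeguard addresses only the puncture site, and the recorded draw site plays no part in the PK population or analyses. For affected samples the error in level is upward; the error in change over time can have either sign.

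Neither the size nor the number of subjects can be settled from the documents. The multiples above are assumptions that show direction and sensitivity, not estimates. The conclusion also depends on the laboratory manual not already restricting the draw site.

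The matter bears on a secondary, exploratory objective and leaves the primary safety and tolerability assessments as they are. It is a cheap improvement worth making.

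**What to change.** **Section 17.3.3.** After unblinding, classify each post-dose PK sample by draw site relative to the subject's Treatment Area, whose body region is already recorded at Baseline:
- active-treated skin lies distal to the draw point on the same limb;
- vehicle-treated skin lies distal to it on the same limb;
- no treated skin lies distal to it.

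Keep the planned summary of all samples. Add a summary by Treatment Group and visit that omits the first class, and flag and list the omitted samples.

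**Section 12.3.** State that the draw site should, where feasible, be one that does not drain a Treatment Area, and otherwise be the same arm at every visit. Record the puncture site on the limb as well as the side, since the example given is only right versus left. Flag Day 84 arm draws in forearm-treated subjects as not separable from local drug. Check the laboratory manual for agreement.

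**Cost.** Wording changes and a slightly fuller entry in an existing field. The restricted summary will have fewer samples. A forearm-treated subject always bled at the same elbow has a 50% chance of contributing no Part 1 post-dose sample to it, and contributes none at Day 84. For that reason the restricted summary should supplement the planned one, not replace it. Analysis alone cannot repair those Day 84 samples; only a draw site that avoids treated skin can. Moving Treatment Areas to the legs is not part of this fix, because it would change where study drug is applied and assessed.
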